6.8.1 Primary Safety Endpoint

The primary safety endpoint of this trial is to evaluate the product safety profile through the assessment of device related adverse events during the study period.

There is no formal hypothesis associated with the primary safety endpoint. Device related adverse events will be tabulated with the number of events and subjects with event for each MedDRA (Version 21.0) SOC/preferred term and overall. Rates will be reported as the number of subjects who experience at least one event out of the total number of subjects.

| Statistical Analysis Plan Pa | | ge 15 of 19 | |
|------------------------------|---|-------------|---------|
| Sponsor | Study | | Version |
| CytoSorbents | CYTOSORB [®] REDUCTION OF FREE HEMOGLOBIN/ACU INJURY (AKI) DURING CARDIAC SURGERY | te Kidney | 1.0 |

6.8.2 Secondary Safety Endpoints

6.8.2.1 Procedure-related Adverse Events

The incidence and severity of procedure-related AEs will be assessed by tabulating the number of events and subjects with event for each event type and overall. Rates will be reported as the number of subjects who experience at least one event out of the total number of subjects. Data will also be tabulated for serious procedure-related AEs. Data will be summarized on the safety population.

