### 6.3.3 Secondary Safety Endpoints

- Incidence and severity of procedure-related adverse events, through 30-days postcardiac surgery.
- Incidence of Serious device-related adverse events
- Incidence and severity of unanticipated adverse device effects (UADEs)
- Change from baseline (pre-procedure) in vital signs (blood pressure, pulse and temperature)
- Change from baseline (pre-procedure) in safety laboratory assessments (hematology with differential, coagulation panel, and comprehensive metabolic panel) pre- and post-cardiac surgery through Day 7 or hospital discharge, whichever occurs first,
- Intra-cardiac surgery arterial blood gas measurements.
- Post-surgical Care Unit assessments (SOFA, vasopressor requirements, blood product transfusions, ventilation requirements, requirement for mechanical support, and renal replacement requirements) through hospital discharge or post-surgical Day 7, whichever occurs first.

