**Investigational Device Related Adverse Event:** An adverse event which, in the judgment of the Investigator, results as a consequence of the investigational device.

**Surgical Procedure Related Adverse Event:** An adverse event which, in the judgment of the Investigator, results as a consequence of the subject's surgical procedure and is not specific to the investigational device used.

**Non-Investigational Device Related Adverse Event:** An adverse event which, in the judgment of the Investigator, it is reasonable to believe that the event is associated with an accessory device used during the surgical procedure and is not specific to the investigational device use.

Grade 1	Mild:	Asymptomatic or mild symptoms; clinical or diagnostic observations only; intervention not indicated.
Grade 2	Moderate:	Minimal, local or noninvasive intervention indicated; limiting age-appropriate instrumental Activities of Daily Living (ADL)*.
Grade 3	Severe:	Severe or medically significant but not immediately life-threatening; hospitalization or prolongation of hospitalization indicated; disabling; limiting self-care ADL**.
Grade 4***	Life- threatening:	Life-threatening consequences; urgent intervention indicated.
Grade 5***	Death:	Death related to AE

Adverse events will also be evaluated for severity based on the following definitions:

\*Instrumental ADL refer to preparing meals, shopping for groceries or clothes, using the telephone, managing money, etc. \*\*Self-care ADL refer to bathing, dressing and undressing, feeding self, using the toilet, taking medications, and not bedridden. \*\*\*Adverse events that are assigned a severity of life-threatening or death will be recorded as Serious Adverse Events.

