### 11.1.1 Safety and Tolerability Evaluations:

The following analyses will be conducted on the Safety population and the two mITT subpopulations.

Continuous safety data will be summarized with descriptive statistics (arithmetic mean, standard deviation [SD], median, minimum, and maximum) by treatment group. Categorical safety data will be summarized with frequency counts and percent of patients by treatment group. Adverse events (AEs) will be coded using the most current Medical Dictionary for Regulatory Activities (MedDRA®) available. A by-participant AE data listing, including verbatim term, preferred term, system organ class, treatment, severity, and relationship to study device will be provided. The number and percent of participants experiencing procedure and device related AEs and serious AEs will be summarized by treatment group, system organ class, and preferred term.

Laboratory evaluations and vital signs assessments will be summarized by treatment group and protocol specified collection time point. A summary of change-from-baseline at each protocol specified time-point by treatment group will also be presented. "Shift Tables" will be provided to summarize count and percent of patients with changes from baseline normal range status (below, within, above) to on/post-treatment normal range status.

Further details regarding presentation and analysis of safety data will be detailed in the statistical analysis plan (SAP).

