6.8.2.3 Unanticipated Adverse Device Effects

The incidence and severity of all unanticipated adverse device effects will be summarized similarly to the primary safety endpoint.

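### SAP 6.8.2.1 and 6.8.2.3 promise incidence and severity of procedure-related AEs and UADEs, but the tabulations they specify contain no severity grade

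*SAP*

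**What the plan says.** Protocol 6.3.3 lists two secondary safety endpoints that each have two components: "Incidence and severity of procedure-related adverse events, through 30-days postcardiac surgery" and "Incidence and severity of unanticipated adverse device effects (UADEs)". In the same list, serious device-related events are named by incidence alone, so severity was attached to particular endpoints.

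Protocol 8.8.1 supplies the scale, with five grades from mild to death: "Adverse events will also be evaluated for severity based on the following definitions". A footnote to that table has life-threatening and fatal events (Grades 4 and 5) recorded as serious adverse events.

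For output, Protocol 11.1.1 plans that "procedure and device related AEs and serious AEs will be summarized by treatment group, system organ class, and preferred term". It puts severity in a listing: "A by-participant AE data listing, including verbatim term, preferred term, system organ class, treatment, severity, and relationship to study device will be provided". It leaves further detail on safety presentation to the SAP.

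The SAP then specifies:

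- 6.8.2.1, procedure-related AEs: "The incidence and severity of procedure-related AEs will be assessed by tabulating the number of events and subjects with event for each event type", followed by "Data will also be tabulated for serious procedure-related AEs".
- 6.8.2.3, UADEs: "The incidence and severity of all unanticipated adverse device effects will be summarized similarly to the primary safety endpoint". The primary safety format in 6.8.1 counts events and affected subjects by MedDRA class and term.
- 6.8.6, total AEs: counts and percentages by seriousness, by severity, and by relationship to the surgical procedure, the investigational device and non-investigational devices.

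**The concern.** Sections 6.8.2.1 and 6.8.2.3 each name severity in their opening sentence and then give a method that cannot measure it. A count of events, or of subjects with at least one event, does not change when events move between grades. A programmer who follows the text would produce the incidence half of each endpoint and nothing for the severity half in that event class.

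This does not look like a deliberate cut. SAP 4.1 explains that analyses were changed after the sponsor stopped the trial early, but these two sections still promise severity. The method does not deliver what its own sentence announces.

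At stake is the by-arm grade distribution of procedure-related AEs, a named secondary safety endpoint. Protocol 8.8.3 expects a range of complications with or without the device. Grade may therefore be an informative part of the comparison, although the documents give no incidence from which to judge how much it would add.

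**Working it through.** No arithmetic applies. The check is whether any planned output gives severity grade, by arm, within the event class that the endpoint names.

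| Planned output | Event class | Grade shown? | Summary by arm? |
|---|---|---|---|
| Protocol 11.1.1 table | Procedure- and device-related AEs, serious AEs | No | Yes |
| Protocol 11.1.1 listing | AEs, by participant | Yes | No, individual events |
| SAP 6.8.2.1, main table | Procedure-related AEs | No | Yes, 6.1.1 default |
| SAP 6.8.2.1, serious table | Serious procedure-related AEs | No | Yes, 6.1.1 default |
| SAP 6.8.2.3, using the 6.8.1 format | UADEs | No | Yes, 6.1.1 default |
| SAP 6.8.6 summary | Total AEs | Yes | Yes, 6.1.1 default |
| SAP 6.8 listings | All AEs, by subject | Columns not specified | No, individual events |

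Three steps follow.

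1. **Main table.** A subject whose only procedure-related event is Grade 1 adds one event and one subject. A subject whose only such event is Grade 3 adds the same. The specified counts cannot tell them apart.

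2. **Serious table.** Seriousness (Protocol 8.8.2) and severity grade (Protocol 8.8.1) are different classifications. By the footnote, every Grade 4 or 5 procedure-related event enters this table. Part of Grade 3 probably enters too, because its definition refers to hospitalization or its prolongation, which is also a seriousness criterion. A Grade 3 event need not qualify, however, and Grades 1 to 3 are not separated in this table or any other for the class.

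3. **Section 6.8.6.** Severity and relationship are listed side by side as separate breakdowns of total AEs. The text does not say that they are crossed. The margins give how many AEs fell in each grade and how many were procedure related, but not how many procedure-related AEs fell in each grade.

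No summary row of the table has both the procedure-related class and the grade.

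**The case against.** The strongest reply is that severity is planned. Section 6.8.6 summarises it, 6.1.1 makes safety tabulations by treatment group by default, and the protocol's listing carries severity, relationship and treatment for each event. All of this stands. A reader might infer from 6.8.2.1 alone that severity is never reported by arm. The documents do not support that, because it is reported for total AEs.

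A second reply is that the serious procedure-related table would reveal much of any severe harm. This also largely stands. A reader might infer that an excess of Grade 3 or higher events in one arm would go unseen. That is too strong: Grades 4 and 5, and probably part of Grade 3, would appear in the serious table, and the main table is broken down by event type. Nor do the documents give a rate to show that any-event incidence would be near its ceiling in both arms.

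A third reply is that the UADE half has little content. A UADE is serious by definition (Protocol 8.8.4), none was reported in REFRESH I (Protocol 2.1), and control subjects do not receive the device. A by-arm grade table for UADEs would be close to empty. This stands, and it limits what is worth asking for there.

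A fourth reply uses SAP 6.8, which counts an AE as procedure related even when the relationship is recorded as unrelated. Read literally, every AE is then procedure related and 6.8.6 already gives the missing breakdown. This does not stand. The definition looks like a drafting error, and the gap returns once it is corrected.

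Finally, the layout might be left to table shells. That would be fair if the SAP were silent, but 6.8.2.1 does state a method for severity, and the method is a count.

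**Conclusion.** The point holds in a limited form. SAP 6.8.2.1 and 6.8.2.3 specify no severity breakdown for two endpoints that the protocol defines partly by severity. Section 6.8.6 covers total AEs only and is not stated to be crossed with procedure-relatedness. The serious procedure-related table includes Grades 4 and 5 but leaves Grades 1 to 3 unseparated.

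The effect is modest. The output is descriptive, the SAP sets no formal hypothesis even for the primary safety endpoint, and grade is collected for each AE, so nothing is lost that a further table cannot recover. The substance lies in the procedure-related endpoint; for UADEs the grade of each event is enough. The gap does not extend to the device-related table in 6.8.1, because the primary safety endpoint in Protocol 6.3.1 does not name severity.

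The conclusion assumes that 6.8.6 means what it says, separate breakdowns, and that the inclusion of unrelated events in SAP 6.8 is an error.

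**What to change.** In SAP 6.8.2.1, add: *Subjects with procedure-related AEs will also be tabulated by worst severity grade (1-5), with number and percent with Grade 3 or higher, by treatment group with roll-ins in parallel.*

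In SAP 6.8.2.3, add: *The severity grade of each UADE will be reported.*

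Correct the relatedness definition in SAP 6.8 at the same time, because the new table depends on which events count as procedure related.

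The cost is a short SAP amendment and one or two extra descriptive tables from data already on the AE form. SAP section 7 provides the route: an amended SAP before the analysis or, if that is no longer possible, a justified description in the clinical study report.

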6.8.2.2 Serious Device-related Adverse Events

The serious device-related adverse events in the study will be summarized similarly to the primary safety endpoint.

6.8.2.3 Unanticipated Adverse Device Effects

The incidence and severity of all unanticipated adverse device effects will be summarized similarly to the primary safety endpoint.

6.8.2.4 Change in Vital Signs

Vital signs include body temperature, heart rate, respiration rate, pulse oximetry, and blood pressure. The observed value of vital signs will be summarized for each visit, starting with admission to the ICU post-procedure, and then daily beginning on Day 1 post-procedure.

The change in vital signs between baseline and Day 1 post-procedure will also be summarized.

6.8.2.5 Change in Laboratory Assessments

Clinical laboratory evaluations include:

- Hematology: white blood cell (WBC) count, red blood cell (RBC) count, hemoglobin, hematocrit, platelet count
- Serum Chemistry: sodium, potassium, chloride, bicarbonate (CO2), BUN (urea), creatinine, serum glucose, calcium, AST (SGOT), ALT (SGPT), alkaline phosphatase, total bilirubin, albumin, total protein
- Coagulation: aPTT, INR, PT, fibrinogen

Clinical laboratory values will be expressed using the standard units (SI).

In the event of repeat values within the same analysis visit, the first measurement at that visit was used.

For hematology and serum chemistry, the observed value and change from baseline will be summarized by visit for continuous clinical laboratory parameter. Shift tables will be provided to summarize count

| Statistical Analysis Plan Pa | | Pa | ge 16 of 19 |
|------------------------------|---|-----------|-------------|
| Sponsor | Study | | Version |
| CytoSorbents | CYTOSORB [®] REDUCTION OF FREE HEMOGLOBIN/ACU INJURY (AKI) DURING CARDIAC SURGERY | te Kidney | 1.0 |

and percent of patients with changes from baseline normal range status (below, within, above) to on/post-treatment normal range status.

6.8.3 Arterial Blood Gas Measurements

Arterial blood gas measurements (PaO², PaCO², pH, HCO³) observed value and change from baseline will be summarized using descriptive statistics at each time point by treatment group and overall, with Roll-ins presented in parallel for patients in the safety population.

FIO2 values were not originally required per protocol. At the request of the DMC, a new field was added to the EDC system to retrospectively collect FIO2 values. Observed values for FIO2 and PaO2/FIO2 Ratio will be summarized using descriptive statistics at each time point by treatment group and overall, with Roll-ins presented in parallel for patients in the safety population.

6.8.4 Blood Product Transfusions

Blood product transfusions are broken into time intervals including intra-operative, post-operative on the day of surgery, day 1 post-surgery, and day 2+ post-surgery (through the end of hospitalization). Data on blood product transfusions will be summarized using descriptive statistics by treatment group and overall, with Roll-ins presented in parallel for patients in the safety population

6.8.5 Additional Post-surgical Care Unit Assessments

Additional post-surgical Care Unit assessments (contributing to the overall health economic summary) include the following through hospital discharge or post-surgical Day 7 (whichever is first): SOFA, vasopressor requirements, requirement for mechanical support, and renal replacement requirements. Data will be summarized using descriptive statistics for each assessment by treatment group and overall, with Roll-ins presented in parallel for patients in the safety population

6.8.6 Additional Safety

The total adverse events in the study will be summarized similarly to the primary safety endpoint. A summary will be presented by seriousness, severity, relationship to surgical procedure, relationship to investigational device, and relationship to non-investigational device will be provided using counts and percentage.

Non-serious adverse events will be tabulated with the number of events and subjects with event for each MedDRA SOC/preferred term and overall. Rates will be reported as the number of subjects who

| Statistical Analysis Plan Pa | | ge 17 of 19 | |
|------------------------------|---|-------------|---------|
| Sponsor | Study | | Version |
| CytoSorbents | CYTOSORB [®] REDUCTION OF FREE HEMOGLOBIN/ACU INJURY (AKI) DURING CARDIAC SURGERY | te Kidney | 1.0 |

experience at least one event out of the total number of subjects. Serious adverse events will be summarized in the same way.

Device deficiencies will be summarized by type of device observation in the safety population.

Subject deaths will be provided in listing format.

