### Table 1: Definitions

Arterial Blood Gas Assessments	Intra-procedure, while patient is on CPB Post-Procedure, only if arterial line is in place
Enrolled	A patient who has provided informed consent to participate in the trial is considered to be enrolled.
Roll-in	The first two enrolled and treated patients at each site used for training purposes. Roll in patients are treated with the CytoSorb device and their data used for safety analysis only.
Randomized	A patient who has been randomly assigned (according to a validated randomization schedule) in a 1:1 ratio to either standard of care (SOC) or SOC with CytoSorb device.
Intra-Cardiac Procedure	During CPB, while on pump
Post-Cardiac Procedure	Following end of CPB
Pre-Procedure	Day of the surgery but before induction of general anesthesia, exclusive of sedation.
Screening	Time-period to determine eligibility, not more than 14 days prior to day of cardiac surgery. When screening laboratory assessments are obtained on the day of surgery, they may be substituted for the pre-procedure laboratory assessments
Baseline	The start of CPB is defined as baseline for pfHb, C3a, C5a, inflammatory mediator panel, and markers of kidney injury (plasma and urine markers) endpoints.
	Pre-procedure is defined as baseline for all other endpoints.
Start Of CPB	Pump on
End Of CPB	Pump off, just prior to protamine reversal ( $\pm$ 5 minutes)
Post-Surgery Care Unit	Coronary Care Unit, Intensive Care Unit, Step Down Unit
Post-Surgery Care Unit Assessments and Labs	Day 1 assessments start at or after midnight post-cardiac surgery. Assessments and lab blood draw times should be approximately the same time each day (see Schedule of Assessments for specific assessments and labs, as well as approved windows).

Abbreviation/Term	Definition
ABG	Arterial blood gas
ADL	Activities of Daily Living
AE	Adverse Event
AKI	Acute kidney injury
ALT	Alanine aminotransferase
APTT	Activated partial thromboplastin time
ARDS	Acute respiratory distress syndrome
AST	Aspartate aminotransferase
AUC	Area under the concentration by time curve
BP	Blood pressure
C3a	Serum complement component C3a
C5a	Serum complement component C5a
CABG	Coronary artery bypass graft
CFR	Code of Federal Regulations
CKD	Chronic kidney damage
СРВ	Cardiopulmonary bypass
CRF	Case Report Form
CRO	Contract research organization
CRP	C-reactive protein
DMC	Data monitoring committee
DMP	Data management plan
ECG	Electrocardiogram
ECMO	Extracorporeal membrane oxygenation

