### 8.4 Screening Visit

Written informed consent will be obtained from the subject (or legally acceptable representative on behalf of the subject) before any study-specific procedures are performed. (Note: Consent by a legally acceptable representative is allowed where applicable, and is in accordance with local laws, regulations, and ethics committee policy.) Subjects are considered enrolled once they sign the informed consent. Screening laboratory samples may be obtained up to 14 days prior to the date of surgery, so that results are available for review at the visit.

Patients are qualified for study participation during the screening period by confirmation of meeting all the inclusion criteria and none of the exclusion criteria. Evaluation of inclusion criterion 2 is based upon the intended surgical procedure during the screening period. During the pre-procedure and intra-operative periods, the intended procedure may change due to factors that could not be adequately determined or anticipated in advance of the procedures. These day-of-surgery changes to intended procedures may result in completion of a procedure that does not align with the eligibility criteria as detailed in inclusion 2. Since eligibility is assessed based on the intended procedure during the screening period, a change on the operative day is not considered a protocol deviation. Patients who have changes to their intended procedures on the day of surgery are study subjects and should progress through the study as detailed in the protocol. These subjects will be included in the Intent-to-Treat analysis.

The following procedures will be performed, and results recorded in the electronic Case Report Forms (eCRF):

- The investigator / designee will solicit a written informed consent from the subject (or legally acceptable representative on behalf of the subject) for study participation.
- Eligibility based on inclusion / exclusion criteria will be assessed.
- Medical history will be reviewed relative to the inclusion/exclusion criteria.
- Demographic details (age, gender, and race).
- Prior and concomitant medications taken during the past 60 days inclusive of any IV contrast agents administered within 48 hours of the procedure
- Complete physical examination
- Vital signs (HR, BP, Temp.) after 5 minutes supine
- Height and weight

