### 8.7 Day 30 Post-Cardiac Surgery

The subjects will be contacted via telephone at 30 days post-cardiac surgery for assessment of the following since hospital discharge:

- Blood product transfusions
- Adverse events

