### 8.8 Safety/Device Assessment

### 8.8.1 Adverse Events

Throughout the study, the Investigator or designee will determine adverse event (AE) occurrences. An adverse event is any untoward medical occurrence (signs, symptoms, abnormal laboratory findings) in a subject regardless of relationship to the device or procedure. Each adverse event is considered to be either anticipated or unanticipated as described below. AEs occurring after the initiation of treatment (start of CPB) are considered to be treatment emergent. The site is required to report the classes of Adverse Events that occur in the study, described below.

Any AEs and remedial action required will be recorded in the patient's source data. The nature, time of onset, duration, and severity will be documented, together with an Investigator's (or designee's) opinion of the relationship to investigational device. Since the incidence and severity of AKI, as defined by KDIGO clinical practice guidelines, are the primary endpoints of the study, the presence of AKI should not be reported as an AE in the trial.

If an AE occurs, appropriate diagnostic and therapeutic measures are to be taken. Follow-up evaluations of the patient are to be performed until the patient recovers or until the clinical Investigator considers the situation to be no longer clinically significant.

Adverse events are monitored and registered on the AE form of the eCRF at each visit. Whenever possible, a specific diagnosis should be entered as the AE term. Outcomes and severity of the AE are not to be recorded as the AE term. In absence of a specific diagnosis, an individual AE form has to be filled in for each sign or symptom. Changes from baseline laboratory values which are abnormal values and that are classified as clinically significant by the investigator must be recorded as AEs.

Persistent AEs will be entered once in the eCRF until they are resolved or if a new event has to be documented due to deterioration. These AEs will be carefully monitored. If an AE is still not resolved at the end of the investigation, this will be documented as ongoing.

For recurrent AEs (i.e., AEs of the same nature, but with a different date of onset), an individual AE form has to be completed for each of them.

Adverse events will be assessed for a relationship to each of the following and relationship classified as unrelated, possible, probable, definite or unknown:

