6.2 Analysis Populations

The following subject populations will be evaluated and used for presentation and analysis of the data:

| Statistical Analysis Plan | | Pa | ge 11 of 19 |
|---------------------------|---|----|-------------|
| Sponsor | Study | | Version |
| CytoSorbents | orbents CytoSorb [®] REduction of FREe Hemoglobin/Acute Kidney Injury (AKI) during Cardiac Surgery | | 1.0 |

• Intent-to-Treat (ITT): All randomized patients.

Safety (SAF): Comprised of all roll-in and randomized subjects in whom treatment was attempted. Safety analysis will be performed on this population. Patients will be summarized according to the actual treatment received, with Roll-in subjects presented in parallel.

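### SAP 6.8.6 tabulates total, serious and non-serious adverse events with no onset condition, so events before bypass dilute the descriptive safety comparison

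*SAP*

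**What the plan says.** **Collection.** The AE row of Protocol Table 3 starts when the patient signs the consent form and runs to study exit. Protocol 8.4 confirms the starting point: "Subjects are considered enrolled once they sign the informed consent". Protocol Table 1 describes screening as "Time-period to determine eligibility, not more than 14 days prior to day of cardiac surgery". Follow-up for AEs ends with a telephone contact (Protocol 8.7): "The subjects will be contacted via telephone at 30 days post-cardiac surgery", with a window of 5 days either side in Table 3.

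**Definition.** Protocol 8.8.1: "AEs occurring after the initiation of treatment (start of CPB) are considered to be treatment emergent". Table 1 sets the start of CPB at pump on, so induction of anesthesia and the surgery before bypass fall on the pre-treatment side.

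**Tabulation.** SAP 6.8.6: "The total adverse events in the study will be summarized similarly to the primary safety endpoint". Non-serious and serious AEs are then tabulated by system organ class and preferred term. The rate rule, given in SAP 6.8.1 and repeated in 6.8.6, is: "Rates will be reported as the number of subjects who experience at least one event out of the total number of subjects". Neither section mentions onset relative to CPB.

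**Population.** SAP 6.2 defines the Safety population as "Comprised of all roll-in and randomized subjects in whom treatment was attempted". This selects patients, not events.

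**Status of the comparison.** SAP 6.8.1: "There is no formal hypothesis associated with the primary safety endpoint".

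**The concern.** The protocol defines a term that separates events that could follow treatment from events that could not, and neither analysis section uses it. Protocol 11.1.1 leaves further detail of the safety presentation to the SAP, so the SAP is where the term would be expected to appear. Other safety data in the SAP are anchored in time: transfusions by interval (6.8.4), vital signs from ICU admission (6.8.2.4) and laboratory shifts to on- or post-treatment status (6.8.2.5). The overall AE tables are not.

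The stake is the readability of the safety comparison. A patient with any event before bypass already counts as having an event, so a later event cannot change that patient's status in the any-event row. With a similar pre-CPB background in both arms, a real excess of events with the device would look smaller than it is. For a safety comparison that is the non-conservative direction. The study stopped at 151 enrolled patients including roll-ins (SAP 4.1), and these descriptive tables carry much of its safety evidence.

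**Working it through.** The plan states no AE rate and no safety sample size, so it has no figure of its own to reproduce. The check has three parts.

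**1. Does anything in the SAP supply the filter?**

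- SAP 6.2 (Safety population): restricts patients only.
- SAP 6.1.2 (study day): assessment date minus procedure date, with no exclusion of negative days.
- SAP 6.8.1 and 6.8.6 (rate rule): any patient with at least one event, with no onset condition.
- Protocol 11.1.1: also has no treatment-emergent restriction.

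Nothing supplies it. That the tables run from consent is not written in the SAP; it follows from SAP 6.8.6 read with Protocol Table 3.

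**2. How long can the pre-treatment window be?**

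- Maximum screening, 30-day follow-up: 14 / (14 + 30) = 14/44 = 32% of calendar time.
- Maximum screening, follow-up call at day 35: 14 / (14 + 35) = 14/49 = 29%.
- Consent 5 days before surgery (assumed): 5 / (5 + 30) = 5/35 = 14%.
- Screening completed on the day of surgery, which Table 1 and Protocol 8.5.2 allow: a matter of hours.

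**3. What does a pre-CPB background do to the tables?**

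Let p be the post-CPB incidence in an arm and b the pre-CPB incidence. Assume b is the same in both arms and independent of later events. Then

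- tabulated incidence = 1 − (1 − p)(1 − b);
- tabulated risk difference = (1 − b) × (true difference);
- the tabulated risk ratio moves toward 1.

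Example with assumed p = 20% (control) and 30% (device) and b = 10%: control 1 − 0.80 × 0.90 = 28%; device 1 − 0.70 × 0.90 = 37%; difference 9 points; ratio 0.37/0.28 = 1.32.

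Risk ratios over a range of assumed values:

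| Assumed post-CPB incidence | b = 0 | b = 2% | b = 5% | b = 10% | b = 20% |
|---|---|---|---|---|---|
| 10% vs 20% | 2.00 | 1.83 | 1.66 | 1.47 | 1.29 |
| 20% vs 30% | 1.50 | 1.45 | 1.40 | 1.32 | 1.22 |
| 40% vs 50% | 1.25 | 1.24 | 1.22 | 1.20 | 1.15 |

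In all three rows the true difference of 10 points shrinks to 9.8, 9.5, 9.0 and 8.0 points at b = 2%, 5%, 10% and 20%.

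Counts of events behave differently. If each arm averages β pre-CPB events per patient, the expected difference is (λ_device + β) − (λ_control + β) = λ_device − λ_control, which is unchanged. The dilution affects the columns that count patients, not the difference in event counts.

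**The case against.** **The SAP breaks no analysis rule.** Protocol 11.1.1 also summarizes AEs without a treatment-emergent restriction, so an all-AE table is permitted. This stands. The gap is a defined term left unused, not a contradiction between the documents.

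**The effect may be small.** The pre-CPB incidences above are assumed. A reader might take the 32% as the share of AEs that precede treatment, but it is the maximum share of calendar time, and the documents give no event rate for either period. Tables are by preferred term, and a term is diluted only by pre-CPB events coded to that same term. Sampling error is also much larger. Suppose all 151 patients had been randomized, about 75 per arm. The standard error of the difference at 28% versus 37% is then √[(0.28 × 0.72 + 0.37 × 0.63)/75] = √(0.4347/75) = 7.6 points, against a dilution of 1 point, and larger with fewer randomized. This stands too, though the dilution is systematic and cheap to remove.

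**The device-related tables.** A reader might infer that the primary safety table and the serious device-related table are diluted in the same way. An event days before device use would ordinarily be graded unrelated to the device. Such events enter those tables only because the relatedness rule in SAP 6.8 lists unrelated and unknown among the categories that count as related. That is a separate defect.

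**The procedure-related table.** A reader might infer that this table should also be cut at the start of CPB. The documents do not support that. Protocol 6.3.3 sets the endpoint through 30 days with no CPB starting point, and Protocol 8.8.1 ties relatedness to the surgical procedure. An event between incision and pump on can qualify. It is also too strong to say that nothing before pump on can involve the device, because Protocol 3.5 has the circuit connected before the procedure begins.

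**Onset times may be missing.** Protocol 8.8.1 has time of onset documented, but Protocol 8.9.1 names only the start date for reporting to the sponsor. A filter on date and time cannot be assumed to work for day-of-surgery events. This stands and shapes the fix.

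**Conclusion.** The point holds for the total, serious and non-serious AE tables in SAP 6.8.6. They have no onset condition, collection starts at consent, and the protocol's own definition of treatment-emergent is not applied. The direction is toward no difference for patient-level incidence differences and ratios.

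The size cannot be computed from the documents. At an assumed 20% versus 30% post-CPB incidence, the risk ratio of 1.50 becomes 1.45 with a 2% pre-CPB incidence and 1.32 with 10%. This rests on equal pre-CPB incidence in the two arms and independence from later events. If few events precede bypass, the effect is negligible.

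No hypothesis test is affected, and the expected difference in event counts does not change. By-subject listings of all AEs (SAP 6.8) would still let a reader find events dated before surgery. This is a low-cost improvement to a descriptive comparison, not a flaw that invalidates the safety analysis.

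**What to change.** In SAP 6.8.6:

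1. Base the total, serious and non-serious AE tables on treatment-emergent events as defined in Protocol 8.8.1, with the same clock in both arms and in the roll-in patients.
2. Show events before the start of CPB in a separate table by arm, so that no event is lost.
3. State a rule for day-of-surgery events with no recorded onset time, for example counting them as treatment-emergent.

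In SAP 6.8.2.1, keep the procedure-related table unrestricted and split it into onset before and after the start of CPB.

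The relatedness rule in SAP 6.8 needs its own correction; this change does not replace it.

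Cost: one flag, a few sentences in the SAP and a small amount of extra programming. CPB start time is already recorded in both arms (Protocol 8.5.3.1 and 8.5.3.2). The downside is that some day-0 events will be classified by convention rather than by observed time.
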